3.0 RESEARCH PARTICIPANT ELIGIBILITY CRITERIA AND STUDY ENROLLMENT

According to institutional and NIH policy, the study will access research participants regardless of gender and ethnic background. Institutional experience confirms broad representation in this regard.

3.1. Inclusion Criteria

Male or female child, age 2 to 8 years (inclusive) at the time of enrollment.

Parent or legal guardian willing and able to give informed consent and comply with study requirements.

3.2. Exclusion Criteria

Current use of investigational or immunosuppressive drugs (e.g., steroids) at the time of enrollment

Currently taking a daily (routine) vitamin A, D, or multivitamin. Note: participants who report occasional or sporadic vitamin use will be allowed to enroll.

History of lung disease, asthma, immunodeficiency, sickle cell disease, or any other serious underlying condition or disease in the opinion of the principal investigator.

Evidence of developmental delay or evolving neurological disorders at screening.

Current use of antibiotics or antivirals at enrollment.

History of having a severe allergy to eggs or to any inactive ingredient in the Influenza virus vaccine

History of a life-threatening reaction to influenza vaccinations

Currently wheezing at the time of enrollment

History of Guillain-Barre Syndrome

History of heart, kidney, or lung conditions

History of diabetes

Use of an anti-influenza medication (including amantadine, rimantadine, oseltamavir, and zanamivir) within 14 days prior to enrollment

Acute febrile [>100.0°F (37.8°C) oral] illness or acute respiratory illness (e.g., cough or sore throat) within 3 days prior to enrollment

Previous receipt of current seasonal influenza vaccine

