3.4. Enrollment on Study at St. Jude

A member of the study team will confirm potential participant eligibility as defined in Section 3.1-3.2, complete and sign the ‘Participant Eligibility Checklist’. The study team will enter the eligibility checklist information into the Patient Protocol Manager (PPM) system. Eligibility will be reviewed, and a research participant-specific consent form and assent document (where applicable) will be generated. The complete signed consent/assent form(s) must

be faxed or emailed to the CPDMO at [name] to complete the enrollment process.

The CPDMO is staffed 7:30 am-5:00 pm CST, Monday through Friday. A staff member is on call Saturday, Sunday, and holidays from 8:00 am to 5:00 pm. Enrollments may be requested during weekends or holidays by calling the CPDMO “On Call” [contact]) or referencing the “On Call Schedule” on the intranet).

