4.2. Contraindications to an influenza virus vaccine

[figure not shown]
Influenza virus vaccine will not be administered to anyone with previously known allergic reaction (e.g., anaphylaxis) to any component of the vaccine, or after a previous dose of any influenza vaccine during the same season prior to study participation.

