5.0 DRUG/DEVICE/BIOLOGIC AGENT INFORMATION

5.1. Influenza Virus Vaccine

The influenza virus vaccine can be of any licensed brand, preferably Fluzone.

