5.2. Vitamin A and D3 Nutritional Supplements, Oral

Vitamin A palmitate 20,000 International Units and Vitamin D3 2,000 International Units liquid formulations will be compounded with gelatin base, tangerine oil, polysorbate 20F, citric acid anhydrous USP, and steviol glycosides 95% into a chewable gummy. The gummies will be compounded for participants by Regal PharmaLab (a local compounding pharmacy) following U.S. Pharmacopeial Convention (USP) 795 good compounding practices for pharmaceutical compounding of nonsterile preparations.

The expiration date will be listed on the product label for storage at controlled room temperature. Individual doses will be dispensed with participant name, medical record number, dosing instructions, and date. St. Jude Children's Research Hospital Pharmacy will dispense the gummies and keep accountability records as per randomized assignment.

Certificates of Analysis (CoA) are available for the Vitamin A palmitate liquid, Vitamin D3 liquid, gelatin base, tangerine oil, polysorbate 20 NF, citric acid anhydrous USP, and steviol glycosides 95%. As vitamin supplements, these products are not FDA approved for prevention, diagnosis or treatment of disease.

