5.3. Matched Placebo

Placebo gummies will be compounded for participants by Regal PharmaLab (local compounding pharmacy) following U.S. Pharmacopeial Convention (USP) 795 good compounding practices for pharmaceutical compounding of nonsterile preparations. The placebo gummies will be formulated with gelatin base, tangerine oil, polysorbate 20 NF, citric acid anhydrous USP, and steviol glycosides 95% and will match the Vitamin A and D3 gummies in shape, taste, texture, and appearance.

The expiration date will be listed on the product label for storage at controlled room temperature. Individual doses will be dispensed with participant name, medical record number, dosing instructions, and date. St. Jude Children's Research Hospital Pharmacy will dispense the gummies and keep accountability records as per randomized assignment.

Certificates of Analysis (CoA) are available for the gelatin base, tangerine oil, polysorbate 20 NF, citric acid anhydrous USP, and steviol glycosides 95%.

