6.1. Screening Visit

At the screening visit, after informed consent is obtained the following will be completed:

Medical History to include:

- History of a severe allergy to eggs or to any inactive ingredient in the influenza virus vaccine
- History of a life-threatening reaction to influenza vaccinations
- History of Guillain-Barre syndrome
- Currently wheezing or history of wheezing if under 5 years old
- History of immunodeficiency
- History of heart, kidney, or lung problems
- History of diabetes
- Currently taking Tamiflu, Relenza, Amantadine, and/or Rimantadine
- Currently taking daily vitamin or multivitamin

Laboratory Evaluations

- Serum for vitamin studies
- Serum for immunologic studies

Questionnaires

- Socio-demographic questionnaire

Once screening criteria is confirmed and vitamin A retinol protein levels have been resulted, the participant will be randomized.

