6.5. Special Instructions and Definitions of Evaluations

Study Visit Windows

Day 0 (Vaccine dose #1) visit must occur within 10 days of screening.

Day 28 (Vaccine dose #2) visit must be performed within +3 days of the protocol specified date

Day 56 (follow-up)visit must be performed within +/- 7 days of the scheduled protocol visit date.

Vaccination

Influenza virus vaccines will be administered per manufacturer's recommendations by trained study or clinic staff.

Participant caregivers will be informed to contact their child's PCP should any influenza virus vaccine related reactions occur over the course of the study.

Vitamins A and D3

Chewable vitamin supplements or placebo gummies will be administered orally to participants prior to receiving the influenza virus vaccine on Day 0 and Day 28 by study staff. The gummy will be administered and documented in the participants research record prior to the influenza virus vaccine vaccination..

Laboratory Evaluations

Immune responses (inclusive of IgM, IgG, IgA, and cytokines) will be measured in blood serum collections at Screening, Day 28, and Day 56. ELISAs and functional assays (neutralization or HAI assays) will examine virus-specific and total antibodies. Serum vitamins A and D will be tested by HPLC and/or tests standardized against HPLC, and with a surrogate retinol binding protein assay.

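### No exclusion criterion or screening question covers allergy to the gummy's ingredients, although both arms chew the gummy on Day 0 and Day 28

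*Combined protocol and SAP*

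**What the plan says.** Section 3.2 has two exclusions on allergy or reaction. One is "History of having a severe allergy to eggs or to any inactive ingredient in the Influenza virus vaccine"; the other is a past life-threatening reaction to influenza vaccination. The screening history in 6.1 repeats both, the first as "History of a severe allergy to eggs or to any inactive ingredient in the influenza virus vaccine". Section 3.4 ties enrollment to these criteria: "A member of the study team will confirm potential participant eligibility as defined in Section 3.1-3.2".

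The study product is described elsewhere. Under 5.2 the vitamins are "compounded with gelatin base, tangerine oil, polysorbate 20F, citric acid anhydrous USP, and steviol glycosides 95% into a chewable gummy". Under 5.3, "The placebo gummies will be formulated with gelatin base, tangerine oil, polysorbate 20 NF, citric acid anhydrous USP, and steviol glycosides 95" percent. Section 6.5 states that vitamin or "placebo gummies will be administered orally to participants prior to receiving the influenza virus vaccine on Day 0 and Day 28".

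Two further statements bear on the point. Section 5.1: "The influenza virus vaccine can be of any licensed brand, preferably Fluzone". Section 4.2, the protocol's only contraindication section: "Influenza virus vaccine will not be administered to anyone with previously known allergic reaction (e.g., anaphylaxis) to any component of the vaccine".

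**The concern.** The protocol screens for allergy to the licensed vaccine but not for allergy to the compounded product that the trial itself adds. The placebo has the same base as the vitamin gummy, so allocation to control does not protect an allergic child. The participants are healthy children aged 2 to 8, so a foreseeable reaction to an ingredient that the parent already knew about is hard to justify.

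A smaller, related mismatch lies between 3.2 and 4.2. On plain wording, 3.2 removes only children with severe or life-threatening vaccine-related allergy, whereas 4.2 withholds vaccine after any known allergic reaction to a component. A child can therefore be eligible under 3.2 and contraindicated under 4.2.

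**Working it through.** No formula applies and the plan states no figure to reproduce. The check sets the lists side by side.

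**What is screened for**

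| Place | Items in list | On allergy or reaction | Naming the gummy or its ingredients |
|---|---|---|---|
| 3.2 Exclusion Criteria | 14 | 2, both vaccine-related | 0 |
| 6.1 Screening Visit, medical history | 9 | 2, both vaccine-related | 0 |
| 4.2 Contraindications | vaccine only | vaccine components | 0 |

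**What is given**

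| Ingredient | Vitamin gummy (5.2) | Placebo gummy (5.3) | Named in 3.2 or 6.1 as an allergy |
|---|---|---|---|
| Gelatin base | yes | yes | no |
| Tangerine oil | yes | yes | no |
| Polysorbate 20 | yes | yes | no |
| Citric acid | yes | yes | no |
| Steviol glycosides | yes | yes | no |
| Vitamin A palmitate, vitamin D3 | yes | no | no |

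Of the five shared base ingredients, 0 are screened for.

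**Can the vaccine-ingredient item stand in?** Only by chance. It is limited to severe allergy. It would cover a gummy ingredient only if that ingredient were also in the vaccine. Section 5.1 allows any licensed brand and the protocol lists no vaccine ingredients, so the overlap cannot be established from the documents.

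**Exposure.** Each child is due two gummies, one at each vaccination visit.

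- Accrual of about 100 (synopsis, 11.3): 100 × 2 = 200 gummies at most.
- Allocation of 40 + 40 (synopsis table, 3.5): 80 × 2 = 160 gummies.
- First exposures, where a prior screen matters most: 80 to 100 children.

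**Timing of the 3.2 and 4.2 mismatch.** Note d of Appendix I places randomization before any Day 0 evaluation. A child whose milder vaccine-component allergy is recognized only when 4.2 is applied at Day 0 has therefore already been allocated.

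**The case against.** The strongest reply is that several safeguards already exist.

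- Section 3.2 lets the principal investigator exclude a child for another serious underlying condition, and a known severe allergy could be put under that heading.
- The 6.1 list can be read as minimum content, and Appendix I requires a medical history at screening and again at the first vaccine visit. A general history might bring up a food or excipient allergy.
- Chewing is supervised by staff. The 30-minute observation after vaccination also covers the period after the gummy.
- A child who reaches Day 28 has already taken one gummy and has an interim history taken.
- The consent pages are not available for review and may tell parents what the gummy contains.

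These points lower the likely harm, and 200 doses is a ceiling rather than an expectation. None of them is a screen for this allergy. Discretion cannot act on an allergy that nobody asked about, and an open history depends on the parent volunteering it. Supervision and observation help manage a reaction but do not prevent it. Whatever the consent form says, section 3.4 checks eligibility against 3.1 and 3.2.

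Later safety data may not reveal the problem reliably either. The gummy is given just before the vaccine, and sections 6.0 and 9.2 exclude vaccine-related adverse events from recording. A gummy reaction attributed to the vaccine could go unrecorded. That is an inference from the text, not something it states.

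On the secondary point, it is fair to say that 4.2 works at the point of administration, gives anaphylaxis as its example and errs toward safety. The wording still differs, but few children would be affected.

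**Conclusion.** The concern holds. As written, a child with a known allergy to a gummy ingredient is eligible, and no listed screening question would identify that child before dosing in either arm. The exposure is up to 200 gummies at the stated accrual, or 160 on the 40 + 40 allocation. The documents give no allergy prevalence and none is assumed, so the number of children at risk is unknown and may be small.

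This is a participant-safety gap that should be closed, softened but not removed by the existing safeguards. It has no claimed consequence for power, sample size or bias. The mismatch between 3.2 and 4.2 is real but narrow; its only cost is that an eligible, randomized child may be found contraindicated after allocation. The conclusion rests on the protocol text and assumes that no unseen page adds an eligibility criterion.

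**What to change.** 1. Add an exclusion to 3.2: known allergy to any ingredient of the vitamin or placebo gummy (vitamin A palmitate, vitamin D3, gelatin, tangerine oil, polysorbate 20, citric acid, steviol glycosides).
2. Add the same item to the 6.1 medical history so that it is asked before randomization.
3. Carry the 4.2 vaccine contraindication, as worded there, into 3.2 and 6.1 so that it is applied at screening rather than after allocation.

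The cost is one exclusion line, one history question and an alignment of wording, with the eligibility checklist updated to match. The downside is a few possible extra screen failures, whose number the documents do not allow to be estimated. Listing any known allergy rather than only severe allergy is the cautious choice for healthy children. Restricting it to severe allergy would exclude fewer children but leave part of the gap open.

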3.3. Research Participant Recruitment and Screening

Children ages 2 to 8 years old will be sought in the Memphis community from a variety of both private and public venues through active recruitment by study staff as well as self-referral in response to advertisements. Types of advertisements that may be used include flyers, postcards, brochures, and newspaper ads.

Advertisements may be distributed in many ways including email, mass mailings, and in person by study staff. Verbal permission will be sought at private locations where advertisements will be posted by study staff and a signed letter of authorization will be obtained from any performance sites where recruitment activities take place. All recruitment materials will be approved by the IRB before use. Advertisements will indicate the nature of the study and provide a phone number for further information.

Study investigators or their designees will explain the study to potential research participants, including eligibility and exclusion criteria. Persons who indicate they are interested in participating in the study and potentially eligible will be offered a screening visit.

During the screening visit, study investigators or their designees will assign a participant ID and provide individuals with information about the study and an opportunity to ask questions. Written informed consent for study participation will be obtained from the parent or legal guardian. Participants who fail the screening process due to the time sensitive criteria (e.g., recent febrile illness) will be allowed to rescreen.

3.4. Enrollment on Study at St. Jude

A member of the study team will confirm potential participant eligibility as defined in Section 3.1-3.2, complete and sign the ‘Participant Eligibility Checklist’. The study team will enter the eligibility checklist information into the Patient Protocol Manager (PPM) system. Eligibility will be reviewed, and a research participant-specific consent form and assent document (where applicable) will be generated. The complete signed consent/assent form(s) must

be faxed or emailed to the CPDMO at [name] to complete the enrollment process.

The CPDMO is staffed 7:30 am-5:00 pm CST, Monday through Friday. A staff member is on call Saturday, Sunday, and holidays from 8:00 am to 5:00 pm. Enrollments may be requested during weekends or holidays by calling the CPDMO “On Call” [contact]) or referencing the “On Call Schedule” on the intranet).

3.5. Procedures for Identifying and Randomizing Research Participants

Eligibility of research participants will be confirmed by the PI or study team. A study team member will then approach the participant and his or her legal authorized representative regarding the study. If the participant and/or caregiver agree to participate and meet eligibility criteria, the participant will be randomized.

Once informed consent has been obtained and eligibility confirmed, participants will be randomized to receive influenza virus vaccine + Vitamins A & D (n=40) or influenza virus vaccine + placebo (n=40). Randomization will be performed in the SJCRH pharmacy by an unblinded pharmacist, using the randomization program developed by the Department of Biostatistics. In order to ensure similar enrollment numbers within each group, randomization will be restricted with a permuted block randomization design. All eligible participants who are enrolled and receive at least one administration of influenza virus vaccine will be included in the analyses.

4.0 TREATMENT PLAN

4.1. Treatment

This is a single site, pilot, randomized controlled trial in healthy children. The primary and secondary endpoints assessing vaccine-induced and total antibody (IgG and IgA) response and IgA/IgG plus IgA/IgM ratios in the sera as well as the functional antibody response toward influenza virus vaccine in the sera will be measured at Day 28, and 56. Approximately 100 total and 80 evaluable participants will be enrolled equally into two groups over 2 flu seasons, one of which will receive oral vitamins A and D (intervention), while the other group will receive the influenza virus vaccine and placebo gummy (control).

Potential participants will be approached by study staff. Participants who wish to participate in the study will complete the informed consent process prior to conducting the screening evaluations.

Allocation will be stratified by levels of Vitamin A using the surrogate retinol-binding protein (RBP). Vitamin A insufficiency (inclusive of deficiency) will be defined as $\leq 1.05 \mu\text{M}$ or $<22,000 \text{ ng/ml}$ RBP. RBP will be used to stratify participants based on previous mouse and human study demonstrating that vitamin A (for which RBP is a surrogate) is well correlated with IgA. RBP measurements are variable in humans, distributed somewhat equally above and below sufficiency cut-off. In contrast, our clinical work has indicated that study participants in Memphis are largely homogenous for vitamin D measurements in that most of the serum values fall below the sufficiency cut off. After the screening evaluations are obtained, the participant without co-enrolled siblings will be allocated to the intervention or placebo arm , in the pharmacy department, by means of a computerized stratified permuted block method (block size 4: allocation ratio 1:1) provided by the department of biostatistics. Co-enrolled siblings will first be stratified by their screening RBP levels, and then siblings within the same RBP level stratum will be equally assigned to intervention or control to avoid the chance of treatment imbalance, with the use of a computerized stratified permuted block method (block size 2: allocation ratio 1:1).

Participants will be randomized to receive either influenza virus vaccine plus vitamins A and D supplements (n=40) or influenza virus vaccine plus matched placebo. Gummies for the intervention and control arm (placebo) will be provided in the same container by an unblinded pharmacist to maintain blinding. For the purposes of this study, Study Day 0 is defined for each participant as the day that the first influenza vaccine dose is administered. All participants will receive 2 doses of influenza virus vaccine at least 28 days apart.

Children will have the first influenza virus vaccine dose (dose 1) administered on day 0 of the trial, and the second dose (dose 2) administered 28 days later.

Vaccines will be administered by a technique consistent with the manufacturer's specification.

Participants will be observed for 30 minutes following vaccination. Participants will be given a food diary card to record their diet between the Day 0 and Day 56 study visits.

Blood serum samples will be collected from participants at Screening and prior to receiving the influenza virus vaccine on Day 28 as well as during their Day 56 follow-up visit.

Chewable Vitamin or Placebo Administration

Chewable Vitamin A & D3 or Placebo Gummy

The chewable gummy contains either Vitamin A (20,000 International Units) and Vitamin D3 (2,000 International Units) or matched placebo, which should be fully chewed under supervision of study staff with documentation in the participants research record and eMAR (electronic medical administration record). The chewable gummy should be administered prior to receiving influenza virus vaccine vaccination.

If participants have difficulty chewing the gummy, another option is to cut the chewable vitamin in half along score line for easier administration.

4.2. Contraindications to an influenza virus vaccine

[figure not shown]
Influenza virus vaccine will not be administered to anyone with previously known allergic reaction (e.g., anaphylaxis) to any component of the vaccine, or after a previous dose of any influenza vaccine during the same season prior to study participation.

4.3. Concomitant Therapy

Information (including name and indication) regarding medication use by participants will be collected at the time of enrollment. All medications taken from enrollment through Day 56 will also be collected. Concomitant medications reported throughout the course of the study will be recorded including: all prescription medications, over-the-counter preparations, vitamins, nutritional supplements, and herbal preparations.

The use of anti-influenza medications for the prevention of influenza is prohibited during the trial as use of these agents prophylactically may affect culture results. Participants caregivers will be asked to inform study staff should their child require anti-influenza medications while on study. Use of all other concomitant therapies will be allowed.

